11.10.14. Pharmacokinetic Figures

Pharmacokinetic : Figures					
No.	Population	IDSL / TST ID / Example Shell	Title	Programming Notes	Deliverable [Priority]
PK Concentration					
6.01	Fully Treated	PK16a	Individual Free Serum Otelixizumab Concentration-Time Plots (Linear and Semi-Log) by Subject		FA (SAC)
6.02	Fully Treated	PK17	Mean Free Serum Otelixizumab Concentration-Time Plots by Treatment (Linear and Semi-Log)	Use geometric mean for semi-log scale	FA (SAC)
6.03	Fully Treated	PK18	Median Free Serum Otelixizumab Concentration-Time Plots by Treatment (Linear and Semi-Log)		FA (SAC)

11.10.15. ICH Listings

ICH : Listings					
No.	Population	IDSL / TST ID / Example Shell	Title	Programming Notes	Deliverable [Priority]
Randomisation					
01.	Randomised	TA1	Listing of Randomised and Actual Treatments		FA (SAC)
Subject Disposition					
02.	Enrolled	ES2	Listing of Reasons for Study Withdrawal		FA (SAC)
03.	Safety	SD2	Listing of Reasons for Study Treatment Discontinuation		FA (SAC)
04.	Enrolled	DV2	Listing of Important Protocol Deviations		FA (SAC)
05.	Enrolled	SP3	Listing of Exclusions from Any Population		FA (SAC)
06.	Screened	ES7	Listing of Reason for Screen Failure		FA (SAC)
07.	Enrolled	IE3	Listing of Subjects with Inclusion/Exclusion Criteria Deviations		FA (SAC)
Exposure					
08.	Safety	EX3	Listing of Exposure Data	
 List each infusion, we will give duration in minutes (end of infusion – start of infusion). We can omit Dosing Frequency. 	FA (SAC)
Demographics					
09.	Safety	DM2	Listing of Demographic Characteristics		FA (SAC)
10.	Safety	DM9	Listing of Race		FA (SAC)

ICH : Listings					
No.	Population	IDSL / TST ID / Example Shell	Title	Programming Notes	Deliverable [Priority]
11.	Safety	Non-Standard OTHER_L10	Listing of Family History of Cardiovascular Risk		FA (SAC)
12.	Safety	Non-Standard OTHER_L11	Listing of Substance Use		FA (SAC)
Conmeds					
13.	Safety	CM3	Listing of Concomitant Medications	Include ATC/Ingredient	FA (SAC)
14.	Safety	Non-Standard OTHER_L6	Listing of Insulin Use	
 CMCAT = DAILY INSULIN USE 	FA (SAC)
AE					
15.	Safety	AE8	Listing of All Adverse Events		FA (SAC)
16.	Safety	AE7	Listing of Subject Numbers for Individual Adverse Events		FA (SAC)
17.	Safety	AE8CPA	Listing of Serious Adverse Events		FA (SAC)
18.	Safety	AE14	Listing of Reasons for Considering as a Serious Adverse Event		FA (SAC)
19.	Safety	AE8	Listing of Adverse Events Leading to Permanent Discontinuation of Study Treatment or Withdrawal from Study		FA (SAC)
20.	Safety	AE2	Relationship of Adverse Event SOCs, PTs, and Verbatim Text		FA (SAC)
21.	Safety	AE8	Listing of All Adverse Events - Cytokine Release Syndrome Induced Symptoms	
 See Section 11.5.3 for definition 	FA (SAC)

ICH : Listings					
No.	Population	IDSL / TST ID / Example Shell	Title	Programming Notes	Deliverable [Priority]
22.	Safety	AE8	Listing of All Adverse Events – Considered Potentially Associated with EBV Reactivation	
 See Section 11.5.3 for definition 	FA (SAC)
23.	Safety	OTHER_L12	Listing of Epstein-Barr Virus Serology: IgG & IgM and Viral Load: PCR	Please include the following: EBCIGGAS, EBVMSOS, EBCIGGAB, EBVMABZ, EBCIGMAB, EBVDNA	FA (SAC)
LABS					
24.	Safety	LB5	Listing of All Haematology Laboratory Data for Subjects with Abnormalities of Potential Clinical Importance		FA (SAC)
25.	Safety	LB14	Listing of Haematology Laboratory Data with Character Results		FA (SAC)
26.	Safety	LB5	Listing of All Clinical Chemistry Laboratory Data for Subjects with Abnormalities of Potential Clinical Importance		FA (SAC)
27.	Safety	LB14	Listing of Clinical Chemistry Laboratory Data with Character Results		FA (SAC)
28.	Safety	LB5	Listing of All Serology Data		FA (SAC)
29.	Safety	LB14	Listing of Serology Data with Character Results		FA (SAC)
ECG's					
30.	Safety	EG3	Listing of ECG Values of Potential Clinical Importance		FA (SAC)
31.	Safety	EG3	Listing of All ECG Values for Subjects with Any Value of Potential Clinical Importance	Including change from Baseline	FA (SAC)

ICH : Listings					
No.	Population	IDSL / TST ID / Example Shell	Title	Programming Notes	Deliverable [Priority]
32.	Safety	EG5	Listing of Abnormal ECG Findings		FA (SAC)
Vital Signs					
33.	Safety	VS4	Listing of Vital Signs of Potential Clinical Importance		FA (SAC)
34.	Safety	VS4	Listing of All Vital Signs for Subjects with Values of Potential Clinical Importance		FA (SAC)
Pharmacokinetics					
35.	Safety	PK07	Listing of free serum concentration-Time Data		FA (SAC)

11.10.16. Non-ICH Listings

Non-ICH : Listings					
No.	Population	IDSL / TST ID / Example Shell	Title	Programming Notes	Deliverable [Priority]
Study Population, Safety and Efficacy					
36.	Safety	CP_ML1 p	Listing of Dosing Times, Meal Start and End Times on Fed Treatment Days	Classify as Safety for HARP/SAFIRE	FA (SAC)
37.	Safety	Non-Standard Other_L4	Listing of Auto-Antibody Results	Classify as Study Population for HARP/SAFIRE	FA (SAC)
38.	Safety	Non-Standard Other_L3	Listing of Immunogenicity Results	Classify as Safety for HARP/SAFIRE	FA (SAC)
39.	Safety	Non-Standard Other_L1	Listing of C-Peptide & Glucose from Mixed Meal Test	
 List by Parameter Absolute and change from baseline result to be presented. 	FA (SAC)
40.	Safety	Non-Standard Other_L2	Listing of C-Peptide & Glucose from Mixed Meal Test: Derived Parameters	
 List by Parameter Absolute and change from baseline result to be presented. Also include C-peptide response 	FA (SAC)
41.	Safety	Non-Standard Other_L8	Listing of C-Peptide & Glucose from Clamp	
 List by Parameter Absolute and change from baseline result to be presented. 	FA (SAC)

Non-ICH : Listings					
No.	Population	IDSL / TST ID / Example Shell	Title	Programming Notes	Deliverable [Priority]
42.	Safety	Non-Standard Other_L9	Listing of C-Peptide & Glucose from Clamp : Derived Parameters	
 ○ List by Parameter ○ Absolute and change from baseline result to be presented. 	FA (SAC)
43.	Safety	Non-Standard Other_L1	Listing of Insulin Sensitivity Index (Hyperglycemic Clamp), Mean Daily Insulin Usage and %HbA1c	
 • Absolute and change from baseline result to be presented. • Example Other_L1 modified based on endpoint. • Include glycemic response variables 	FA (SAC)
44.	Safety	Non-Standard Other_L5	Listing of Hypoglycemic & Hyperglycemic Event Rates		FA (SAC)
45.	Safety	Non-Standard Other_L7	Cardiovascular Events	Classify as Safety for HARP/SAFIRE	FA (SAC)
Pharmacodynamics					
46.	Safety	Non-Standard Other_L1	Listing of Pharmacodynamics including Target Engagement	
 • Absolute and change from baseline result to be presented. • Example Other_L1 modified based on endpoint. 	FA (SAC)
Biomarkers					

Non-ICH : Listings					
No.	Population	IDSL / TST ID / Example Shell	Title	Programming Notes	Deliverable [Priority]
47.	ITT (Treated)	Non-Standard Other_L1	Listing of frequency and phenotype of lymphocyte subsets by flow cytometry	
 Absolute and change from baseline result to be presented. Example Other_L1 modified based on endpoint. 	FA (SAC)
48.	ITT (Treated)	Non-Standard Other_L1	Listing of frequency of FoxP3 regulatory cells and TH17 cells by epigenetic quantification	
 Absolute and change from baseline result to be presented. Example Other_L1 modified based on endpoint. 	FA (SAC)
49.	Multimer Analyses	Non-Standard Other_L1	Listing of frequency and phenotype of HLA-A2-restricted antigen-specific CD8+ T cells by multimer analysis	
 Absolute and change from baseline result to be presented. Example Other_L1 modified based on endpoint. 	FA (SAC)
50.	ITT (Treated)	Non-Standard Other_L1	Listing of frequency of interferon-gamma-secreting antigen-reactive cells by ELISPOT	
 Absolute and change from baseline result to be presented. Example Other_L1 modified based on endpoint. 	FA (SAC)
51.	ITT (Treated)	Non-Standard Other_L1	Listing of quantification of serum cytokines and soluble cytokine receptors	
 Absolute and change from baseline result to be presented. Example Other_L1 modified based on endpoint. 	FA (SAC)
52.	ITT (Treated)	Non-Standard Other_L1	Listing of TCR deep sequencing results	
 Absolute and change from baseline result to be presented. Example Other_L1 modified based on endpoint. 	FA (SAC)

[figure not shown]
Non-ICH : Listings					
No.	Population	IDSL / TST ID / Example Shell	Title	Programming Notes	Deliverable [Priority]
53.	ITT (Treated)	Non-Standard Other_L1	Listing of suppressive activity of regulatory cells	
 Absolute and change from baseline result to be presented. Example Other_L1 modified based on endpoint. 	FA (SAC)
Statistical Listings					
54.	ITT (Treated)	SAS Output	Statistical Output for Statistical Analysis (MMRM) Results of Change from Baseline : C-Peptide & Glucose Weighted Mean AUC(0-120 mins) from Mixed Meal Tolerance Test	
 Please include standard SAS output, including estimation of variance components, model diagnostics and residual plots Also include a listing showing the p-values for the model selection approach described in Section 9.1.5.1 in the following format: Covariate Type III P-value BMI 0.XXXXXX (from 1) BMI*trt 0.XXXXXX (from 2) Show this for each covariate, but do not include tests for the other variables in the model 	FA (SAC)
55.	ITT (Treated)	SAS Output	Statistical Output for Statistical Analysis (MMRM) Results of Change from Baseline : C-Peptide Weighted Mean AUCs (60-140 mins) from Hyperglycemic Clamp Test	
 Please include standard SAS output, including estimation of variance components, model diagnostics and residual plots 	FA (SAC)

Non-ICH : Listings					
No.	Population	IDSL / TST ID / Example Shell	Title	Programming Notes	Deliverable [Priority]
56.	Fully Treated	SAS Output	Statistical Output for Statistical Analysis (MMRM) Results of Change from Baseline : C-Peptide & Glucose Weighted Mean AUC(0-120 mins) from Mixed Meal Tolerance Test	
 Please include standard SAS output, including estimation of variance components, model diagnostics and residual plots 	FA (SAC)
57.	Fully Treated	SAS Output	Statistical Output for Statistical Analysis (MMRM) Results of Change from Baseline : C-Peptide Weighted Mean AUCs (60-140 mins) from Hyperglycemic Clamp Test	
 Please include standard SAS output, including estimation of variance components, model diagnostics and residual plots 	FA (SAC)
58.	ITT (Treated)	SAS Output	Statistical Output for Statistical Analysis (MMRM) Results of Change from Baseline : Insulin Sensitivity Index from Hyperglycemic Clamp Test	
 Please include standard SAS output, including estimation of variance components, model diagnostics and residual plots 	FA (SAC)
59.	ITT (Treated)	SAS Output	Statistical Output for Statistical Analysis (MMRM) Results of Change from Baseline : Mean Daily Insulin Use	
 Please include standard SAS output, including estimation of variance components, model diagnostics and residual plots 	FA (SAC)
60.	ITT (Treated)	SAS Output	Statistical Output for Statistical Analysis (MMRM) Results of Change from Baseline: %HbA1c	
 Please include standard SAS output, including estimation of variance components, model diagnostics and residual plots 	
61.	ITT (Treated)	SAS Output	Summary of Statistical Analysis (MMRM) Results of Change from Baseline: Body Weight	
 Please include standard SAS output, including estimation of variance components, model diagnostics and residual plots 	

11.11. Appendix 11: Example Mock Shells for Data Displays

Example : EFF_F1
Protocol : OTX116505
Population : Safety

Figure X.XX
Model Adjusted Mean (95% CI) Change from Baseline Plot: C-Peptide & Glucose Weighted Mean AUC(0-120 mins) from Mixed Meal Tolerance Test

[figure not shown]

Programming Notes : [1] Include C-Peptide and Glucose.
[2] Use OTX instead of OTE for treatment labels.

[3] An OTX 36 mg will not be included in the data (not dosed)

Example : EFF_F2
Protocol : OTX116505
Population : Safety

Figure X.XX
Mean (+/- SE) Number of hyperglycemic and hypoglycemic events by month

Programming Notes : [1] Example only; actual event rates are not assumed to stay constant over month.

Example : EFF_F3
Protocol : OTX116505
Population : Safety

Page 1 of X

Figure X.XX

Mean (+/- SE) Change from Baseline in Frequency and phenotype of lymphocyte subsets by flow cytometry by C-Peptide Response

[figure not shown]
Programming Notes :	Similar to EFF_F1, but with: [1] Line by C-Peptide Responder Status [2] Panel by treatment
----------------------------	--

Example : SAF_F1
Protocol : OTX116505
Population : Safety

Page 1 of X

Figure X.XX
Individual Subject Plot - Hematology & Clinical Chemistry Selected Parameters

Category: Hematology; Parameter: Leukocytes (GI/L)
Treatment: Placebo; Time Span: All data

PPD

Programming Notes : Similar to EFF_F1, but with:

[1] Line by C-Peptide Responder Status
[2] Panel by treatment

Example : SAFE_T1

Table SAFE_T1 has been deprecated and will not be used.

Page 1 of 1

Example : **SAFE_T2**
 Protocol : OTX116505
 Population : Safety

Table X.XX
 Summary (Absolute and Change from Baseline) of Epstein-Barr Virus (Viral Load: PCR)

Summary: Absolute

Treatment	Time	N	n	Mean/Geo. Mean	95% Confidence Interval for		Min	Median	Max
					Geometric Mean	CVb%			
Placebo	X	x	x	xxx.x/xxx.x	xxx.x; xxx.x	XX%	xxx	xxx	Xxx
	X	x	x	xxx.x/xxx.x	xxx.x; xxx.x	XX%	xxx	xxx	Xxx
	X	x	x	xxx.x/xxx.x	xxx.x; xxx.x	XX%	xxx	xxx	Xxx

OTX 9 mg	X	x	x	xxx.x/xxx.x	xxx.x; xxx.x	XX%	xxx	xxx	Xxx
	X	x	x	xxx.x/xxx.x	xxx.x; xxx.x	XX%	xxx	xxx	Xxx
	X	x	x	xxx.x/xxx.x	xxx.x; xxx.x	XX%	xxx	xxx	Xxx

Continue for other doses

Programming Notes : [1] For applicable endpoints, include parameter as either a BY parameter or as first column in the table
 [2] CVb%: calculate SD on log scale and then CVb% = 100*sqrt(exp(SD^2)-1) with SD being the SD on log scale.

Example : **SAFE_T2 (Continued)**
Protocol : OTX116505
Population : Safety

Page 1 of X

Table X.XX
Summary (Absolute and Change from Baseline) of Epstein-Barr Virus (Viral Load: PCR)

Summary: Change from Baseline

ETC

Programming Notes : [1] For applicable endpoints, include parameter as either a BY parameter or as first column in the table

Example : SAFE_T3
 Protocol : OTX116505
 Population : Safety

Table X.XX
 Summary of Categorical values of Epstein-Barr Virus (Serology:IgG & IgM)

Parameter	Visit	Treatment	N	n	Number of Subjects (%)					
					Absolute Values		Change from Baseline			
					Positive	Negative	Positive-Positive	Positive-Negative	Negative-Positive	Negative-Negative
Epstein-Barr IgG Antibody	Screening	Placebo	XX	XX	XX (%)	XX (%)				
		OTX 9 mg	XX	XX	XX (%)	XX (%)				
		OTX 18 mg	XX	XX	XX (%)	XX (%)				
		OTX 27 mg	XX	XX	XX (%)	XX (%)				
	Day -1	Placebo	XX	XX	XX (%)	XX (%)				
		OTX 9 mg	XX	XX	XX (%)	XX (%)				
		OTX 18 mg	XX	XX	XX (%)	XX (%)				
		OTX 27 mg	XX	XX	XX (%)	XX (%)				
	Day 6	Placebo	XX	XX	XX (%)	XX (%)	XX (%)	XX (%)	XX (%)	XX (%)
		OTX 9 mg	XX	XX	XX (%)	XX (%)	XX (%)	XX (%)	XX (%)	XX (%)
		OTX 18 mg	XX	XX	XX (%)	XX (%)	XX (%)	XX (%)	XX (%)	XX (%)
		OTX 27 mg	XX	XX	XX (%)	XX (%)	XX (%)	XX (%)	XX (%)	XX (%)

Example : **SAFE_T4**
 Protocol : OTX116505
 Population : Safety

Table X.XX
 Categorical Summary of Epstein-Barr Virus (Viral Load: PCR)

Unit: copies/10⁶PBM cells

Treatment	Visit	N	n	Number of Subjects (%)			
				0-1000	>1000-10000	>10000-100000	>100000
Placebo	X	x		XX (%)	XX (%)	XX (%)	XX (%)
	X	x		XX (%)	XX (%)	XX (%)	XX (%)
	X	x		XX (%)	XX (%)	XX (%)	XX (%)
	.	.					
OTX 9 mg	X	x		XX (%)	XX (%)	XX (%)	XX (%)
	X	x		XX (%)	XX (%)	XX (%)	XX (%)
	X	x		XX (%)	XX (%)	XX (%)	XX (%)
	.	.					
ETC							

Programming Notes : [1] For applicable endpoints, include parameter as either a BY parameter or as first column in the table

Example : EFF_T1
 Protocol : OTX116505
 Population : Safety

Table X.XX
 Summary Statistics (Absolute and Change from Baseline): C-Peptide & Glucose from Mixed Meal Tolerance Test

Parameter: C-peptide Weighted Mean AUC 0-120 mins (nmol/L)

Treatment	N	Visit	Variable	n	Mean	95% Confidence Interval	SD	Min	Median	Max
Placebo	X	Screening	Abs.	X	xxx.x	xxx.x, xxx.x	xx.xx	xxx	xxx	Xxx
		Month 3	Abs.	X	xxx.x	xxx.x, xxx.x	xx.xx	xxx	xxx	Xxx
		XXXX	Chg.	X	xxx.x	xxx.x, xxx.x	xx.xx	xxx	xxx	Xxx
		Month 6	Abs.	X	xxx.x	xxx.x, xxx.x	xx.xx	xxx	xxx	Xxx
		XXXX	Chg.	X	xxx.x	xxx.x, xxx.x	xx.xx	xxx	xxx	Xxx
		XXXX		X	xxx.x	xxx.x, xxx.x	xx.xx	xxx	xxx	Xxx
OTX 9 mg		XXXX		X	xxx.x	xxx.x, xxx.x	xx.xx	xxx	xxx	Xxx
		XXXX		X	xxx.x	xxx.x, xxx.x	xx.xx	xxx	xxx	Xxx
		XXXX		X	xxx.x	xxx.x, xxx.x	xx.xx	xxx	xxx	Xxx
ETC										

Programming Notes : [1] For applicable endpoints, include parameter as either a BY parameter or as first column in the table

Example : **EFF_T1 (Continued)**
Protocol : OTX116505
Population : Safety

Page 1 of X

Table X.XX

Summary Statistics (Absolute and Change from Baseline): C-Peptide & Glucose from Mixed Meal Tolerance Test

Summary: Change from Baseline

Please use same shell as for absolute values

Programming Notes :	[1] For applicable endpoints, include parameter as either a BY parameter or as first column in the table [2] If later it is decided to use log-transformation instead, then please use SAFE T-2 as template for them. [3]: If not all columns fit on one page, please switch to PD_T1 instead.
----------------------------	--

Example : EFF_T2
 Protocol : OTX116505
 Population : Safety

Table X.XX

Summary of Statistical Analysis (MMRM) Results of Change from Baseline: C-Peptide & Glucose Weighted Mean AUC(0-120 mins) from Mixed Meal Tolerance Test

Parameter:

Visit	Statistic	Placebo N=xx	OTX 9 mg N=xx	OTX 18 mg N=xx	OTX 27 mg N=xx
Month 3	n (1)	xx	xx	xx	xx
	n (2)	xx	xx	xx	xx
	LS Mean	x.xx	x.xx	x.xx	x.xx
	LS Mean Change	x.xx	x.xx	x.xx	x.xx
	Standard Error	x.xxx	x.xxx	x.xxx	x.xxx
	Difference from Placebo		x.xx	x.xx	x.xx
	95% Confidence Interval		x.xx - x.xx	x.xx - x.xx	x.xx - x.xx
P-value			0.xxx	0.xxx	0.xxx

Footnotes :	n(1) = Number of subjects in analysis; n(2) = Number of subjects with data at that visit P-value tests the null hypothesis of no difference from placebo.
Programming Notes	Use three decimal places for p-values. Always use ceiling instead of rounding (i.e. show 0.0501 as 0.051 and not 0.050. If the p-value is smaller than 0.001 display as "< 0.001".

Example : EFF_T3
 Protocol : OTX116505
 Population : Safety

Table X.XX
 Summary of Hypoglycaemic & Hyperglycaemic Events and Event Rates

Hypoglycaemic Events

Time Period Category	Placebo (N=xxx)			9mg (N=xxx)		
	n (%)	Number of Events / Mean [1]	Time Normalized Number of Events / Mean [2]	n/N (%)	Number of Events / Mean [1]	Time Normalized Number of Events / Mean [2]
Any Time Post-dose						
Number of Subjects	X			X		
Any Hypoglycemia	xxx (xx%)	xxx / xx.x	xxx / xx.x	xxx/xxx (xx%)	xxx / xx.x	xxx / xx.x
Hypoglycemia Grade 1	xxx (xx%)	xxx / xx.x	xxx / xx.x	xxx/xxx (xx%)	xxx / xx.x	xxx / xx.x
Hypoglycemia Grade 2	xxx (xx%)	xxx / xx.x	xxx / xx.x	xxx/xxx (xx%)	xxx / xx.x	xxx / xx.x
Hypoglycemia Grade 3	xxx (xx%)	xxx / xx.x	xxx / xx.x	xxx/xxx (xx%)	xxx / xx.x	xxx / xx.x
...						
Dosing Period						
Number of Subjects	X			X		
Any Hypoglycemia	xxx (xx%)	xxx / xx.x	xxx / xx.x	xxx (xx%)	xxx / xx.x	xxx / xx.x
Hypoglycemia Grade 1	xxx (xx%)	xxx / xx.x	xxx / xx.x	xxx (xx%)	xxx / xx.x	xxx / xx.x
Hypoglycemia Grade 2	xxx (xx%)	xxx / xx.x	xxx / xx.x	xxx (xx%)	xxx / xx.x	xxx / xx.x
Hypoglycemia Grade 3	xxx (xx%)	xxx / xx.x	xxx / xx.x	xxx (xx%)	xxx / xx.x	xxx / xx.x
..						

[1] Number of Events = the total number of events at each level of summarization. Mean = the average

number of events reported per subject.

[2] Normalized by dividing Number of Events by length of reporting period in month (1 month = 30 days).
Mean = the average event rate reported by subject. Subjects are only included if they had both visits
delimiting the reporting period.

Programming Notes :	[1] Please show same categories as AE tables by grade: grades 1,2,3,4,5 as well as grade 3+4+5 and unknown (if any). [2] Continue with Post-dose up to Week 6 Visit, Post Week 6 Visit to Month 3 Visit, Post Month 3 Visit to Month 6 visit then similarly, 6-9, 9-12, 12-18, 18-24. Please continue with Hyperglycaemic events and update the footnote accordingly. Please use the Number of Subjects row in each column as the denominator for the percentages, not the overall N.
----------------------------	--

Example : EFF_T4
 Protocol : OTX116505
 Population : Safety

Table X.XX
 Number and Percent of Subjects Meeting Definition of Glycemic Responder

	Visit	Responder Status	Placebo N =XX	OTX 9 mg	OTX 18 mg	OTX 27 mg
Glycemic Response	Week 4	Responders	XX (XX%)	XX (XX%)	XX (XX%)	XX (XX%)
		Non-responders	XX (XX%)	XX (XX%)	XX (XX%)	XX (XX%)
		New responders	XX (XX%)	XX (XX%)	XX (XX%)	XX (XX%)
		Non-responders who were responders at previous visit	XX (XX%)	XX (XX%)	XX (XX%)	XX (XX%)
	Week X	...				

Note: a subject is a glycemic responder, if he fulfils the following criteria:
 1. HbA1c <= 7%
 2. Mean daily insulin use < 0.5 units/kg/day.

Example : EFF_T5
 Protocol : OTX116505
 Population : Safety

Table X.XX

Summary Statistics (Absolute and Change from Baseline): Frequency and phenotype of lymphocyte subsets by flow cytometry by C-Peptide Response

Parameter: XXXXX (UNIT)

Summary: Absolute

Visit	Statistic	Placebo N=XX		OTX 9 mg N=XX		OTX 18 mg N=XX		OTX 27 mg N=XX	
		Non-responders	Responders	Non-responders	Responders	Non-responders	Responders	Non-responders	Responders
Screening	n	xx	xx	xx	xx	xx	xx	xx	xx
	Mean	xxx.x	xxx.x	xxx.x	xxx.x	xxx.x	xxx.x	xxx.x	xxx.x
	95% Confidence Interval	xxx.x; xxx.x	xxx.x; xxx.x	xxx.x; xxx.x	xxx.x; xxx.x	xxx.x; xxx.x	xxx.x; xxx.x	xxx.x; xxx.x	xxx.x; xxx.x
	SD	xx.xx	xx.xx	xx.xx	xx.xx	xx.xx	xx.xx	xx.xx	xx.xx
	Min	xxx	xxx	xxx	xxx	xxx	xxx	xxx	xxx
	Median	xxx	xxx	xxx	xxx	xxx	xxx	xxx	xxx
	Max	xxx	xxx	xxx	xxx	xxx	xxx	xxx	xxx
...	...								
ETC									

Programming Notes :	Footnotes: [1] A participant is considered a C-peptide responder if there is >-40% change from baseline in C-peptide MMTT Weighted Mean AUC (0-120) after 24 months.
----------------------------	---

[2] Subjects with missing responder status due to missing C-peptide at 24 months are not included in the table.

Example : PD_T1
Protocol : OTX116505
Population : Safety

Table X.XX
Summary Statistics (Absolute and Change from Baseline): Target Engagement

Parameter: XXXXX

Treatment	N	Visit, Time	Variable	n	Mean	95% Confidence Interval	SD	Min	Median	Max
Placebo	X	Day 1, 00:00	Abs.	X	xxx.x	xxx.x, xxx.x	xx.xx	xxx	xxx	Xxx
			Chg.	X	xxx.x	xxx.x, xxx.x	xx.xx	xxx	xxx	Xxx
...										
OTX 9 mg										
ETC										

Example : OTHER_L1
 Protocol : OTX116505
 Population : Safety

Listing XX
 Listing of C-Peptide & Glucose from Mixed Meal Tolerance Test

Treatment: Placebo

Inv./ Subj.	Age(yrs)/ Sex/ Race	Visit	Date/ Study Day	Planned/Actual Relative Time (Mins)	Time Sample Taken	C-Peptide (Units)	Glucose (Units)
XXXXX/ XXX	XX/ Male/ White	XXXX	DDMMMYYYY / XX	X / X	HH:MM	XXX.XX	XXX.XX
				X	HH:MM	XXX.XX	XXX.XX
				X	HH:MM	XXX.XX	XXX.XX
				X	HH:MM	XXX.XX	XXX.XX
		XXXX	DDMMMYYYY	X	HH:MM	XXX.XX	XXX.XX
				X	HH:MM	XXX.XX	XXX.XX
				X	HH:MM	XXX.XX	XXX.XX

Programming Notes : [1] As required to be modified based on data and any applicable IDSL standard principles for listings

Example : OTHER_L2
 Protocol : OTX116505
 Population : Safety

Listing XX
 Listing of C-Peptide & Glucose from Mixed Meal Test: Derived Parameters

Treatment: Placebo

Inv./Subj.	Age(yrs)/ Sex/ Race	Analyte	Visit	Date/Study Day	Time Int. For Derivation (Mins)	Weighted Mean AUC(0-120M) Results	Change from Baseline Weighted Mean AUC(0-120M)
XXXXX/ XXX	XX/ Male/ White	XXXXX	XXXX	DDMMYYYY / XX	XXX	X.XXX	X.XXX
			XXXX		XXX	X.XXX	X.XXX
			XXXX		XXX	X.XXX	X.XXX
			XXXX		XXX	X.XXX	X.XXX
		XXXXX	XXXX			X.XXX	X.XXX
			XXXX			X.XXX	X.XXX
			XXXX			X.XXX	X.XXX
			XXXX			X.XXX	X.XXX

Programming Notes : [1] As required to be modified based on data and any applicable IDSL standard principles for listings

Example : OTHER_L3
Protocol : OTX116505
Population : Safety

Page 1 of X

Listing XX
Listing of Immunogenicity Results

Treatment: Placebo

Inv./ Subj.	Age(yrs)/ Sex/ Race	Visit	Date/Time sample Taken	Screening Result	Confirmation Result	Titer
Xxxx/ xxx	XX/ Male/ White	Day -1	DDMMYYYY/Hh:mm	Positive	Positive	X

Programming Notes : [1] As required to be modified based on data and any applicable IDSL standard principles for listings

Example : OTHER_L4
Protocol : OTX116505
Population : Safety

Page 1 of X

Listing XX
Listing of Auto-Antibody Results

Treatment:Placebo

Inv./ Subj.	Age (yrs) / Sex/ Race	Visit	Date	Study Day	Time	Result	Unified Classifica tion
Xxxx/ xxx	27/ Male/ White	Screening	DDMMYYYY	XX	XX:XX	XXXX	XXXX

Programming Notes : [1] As required to be modified based on data and any applicable IDSL standard principles for listings

Example : OTHER_L5
 Protocol : OTX116505
 Population : Safety

Listing XX
 Listing of Hypoglycemic & Hyperglycemic Event Rates

Treatment: Placebo

Inv. / Subj.	Age (yrs) / Sex/ Race	Event Type	Reporting Period	Number of Events	Start/End Date of Reporting Period	Duration of reporting period (months)	Event Rate (1/month)
Xxxx/ xxx	27/ Male/ White	Hypoglycemic	Overall (up to 24 months visit) Post-dose Dosing Period	XXXX	DDMMYYYY/ DDMMYYYY	XXX	XXXX
			Post Dosing Period up to 6 weeks	XXXX	DDMMYYYY/ DDMMYYYY	XXXX	XXXX
			6 weeks to 3 months	XXXX	DDMMYYYY/ DDMMYYYY	XXXX	XXXX

Footnotes:	For the purpose of this listing one month is assumed to have 30 days. Duration of period and event rate will only be calculated if the visit at the end of the reporting period took place.
Programming Notes :	[1] As required to be modified based on data and any applicable IDSL standard principles for listings

Example : OTHER_L6
 Protocol : OTX116505
 Population : Safety

Listing XX
 Listing of Insulin Use

Treatment: Placebo

Inv./ Subj.	Age (yrs) / Sex/ Race	Study Day	Date/Time	Reported Name/ Standardized Name	Dose	Unit	Last Recorded Weight Prior to Intake (kg)	Standardized Dose (IU/kg)
Xxxx/ xxx	27/ Male/ White	XXXX	DDMMYYYY/Hh:mm	XXXXX/XXXXX				
		XXXX	DDMMYYYY/Hh:mm					
		XXXX	DDMMYYYY/Hh:mm					
		XXXX	DDMMYYYY/Hh:mm					
		Day -1						
		Mean Use						

Footnotes:	For the purpose of this listing one month is assumed to have 30 days. Duration of period and event rate will only be calculated if the visit at the end of the reporting period took place.
Programming Notes :	[1] As required to be modified based on data and any applicable IDSL standard principles for listings [2] If all units are IU or convertible to IU combine Dose and Unit columns to a single Column Dose (IU)

Example: OTHER_L7
Protocol : OTX116505
Population : Safety

Listing XX
Cardiovascular Events

Treatment	Inv. / Subj.	Age (yrs) / Sex/ Race	Visit	Date	Cardiovascular Events	Events
xxxx	XXXXXX/ XXXXXX	27/ Male/ White	XXX	DDMMYYYY	No Yes	Congestive Heart Failure
					No	Pulmonary Hypertension

Example : OTHER_L8
 Protocol : OTX116505
 Population : Safety

Page 1 of X

Listing XX
 Listing of C-Peptide & Glucose from Clamp

Treatment: Placebo

Inv./ Subj.	Age(yrs)/ Sex/ Race	Visit	Date/ Study Day	Phase	Planned/Actual Relative Time (Mins)	Time Sample Taken	Glucose Infusion Concentration and Rate (ml/hr).	C-Peptide (Units)	Glucose (Units)
XXXXX/ XXX	XX/ Male/ White	XXXX	DDMMMYYYY / XX	Euglycemic	X / X	HH:MM	Gluc 10%, 50ml/hr	XXX.XX	XXX.XX
					X	HH:MM	Gluc 20%, 100 ml/hr	XXX.XX	XXX.XX
					Hyperglycemic	X	HH:MM	NaCl, 50 ml/hr	XXX.XX
		X	HH:MM	...		XXX.XX	XXX.XX		
		X	HH:MM			XXX.XX	XXX.XX		
		XXXX	DDMMMYYYY/XX	X	HH:MM		XXX.XX	XXX.XX	
				X	HH:MM		XXX.XX	XXX.XX	
				X	HH:MM		XXX.XX	XXX.XX	

Programming Notes : [1] As required to be modified based on data and any applicable IDSL standard principles for listings

Example : OTHER_L9
 Protocol : OTX116505
 Population : Safety

Page 1 of X

Listing XX
 Listing of C-Peptide & Glucose from Clamp: Derived Parameters

Treatment: Placebo

Inv./ Subj.	Parameter	Visit	Date/Study Day	Time Int. For Derivation (Mins)	Result	Change from Baseline	
XXXXX/ XXX	Glucose Weighted Mean AUC(60-140M) (UNIT)	XXXX	DDMMMYYYY / XX	XXX	X.XXX	X.XXX	
		XXXX		XXX	X.XXX	X.XXX	
		XXXX		XXX	X.XXX	X.XXX	
	xxxx	XXXX				X.XXX	X.XXX
		XXXX				X.XXX	X.XXX
		XXXX				X.XXX	X.XXX
		XXXX				X.XXX	X.XXX

Programming Notes :	[1] As required to be modified based on data and any applicable IDSL standard principles for listings [2] Include the following parameters: Glucose weighted mean (60-140), C-Peptide weighted mean (60-140), Insulin Sensitivity
----------------------------	--

Example : OTHER_L10
Protocol : OTX116505
Population : Safety

Page 1 of X

Listing XX
Listing of Family History of Cardiovascular Risk

Treatment: Placebo

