5. CONSIDERATIONS FOR DATA ANALYSES AND DATA HANDLING CONVENTIONS

5.1. Study Treatment & Sub-group Display Descriptors

Study Treatment Descriptions			
Code	Description	Description	Order ^[2]
A	Otelixizumab 9 mg	OTX 9 mg	2
B	Otelixizumab 18 mg	OTX 18 mg	3
C	Otelixizumab 27 mg	OTX 27 mg	4
P ^[1]	Placebo	Placebo	1

NOTES :

[1] Placebo will be pooled across cohorts for analysis and reporting.

[2] Order in which treatments are to be presented in Tables, Figures and Listings.

Due to protocol amendments, there have been some changes in the scheduling of certain assessments. Listings will show the visit according to the schedule according to the protocol version used, while for summary tables the following rules shall apply:

- In general, if for an endpoint some participants have a Week 4 assessment, while other subjects have a Month 1 assessment (e.g. mean insulin usage), it will be summarized under Week 4.
- For vital signs, haematology, clinical chemistry, biomarkers and Epstein-Barr virus serology, the time points Month 1 and Week 6 shall be combined and displayed as "Month 1/Week 6" with an explanatory footnote.

Treatment comparisons will be displayed as follows using the descriptors as specified:

1. OTX 9 mg vs Placebo
2. OTX 18 mg vs Placebo
3. OTX 27 mg vs Placebo

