11.3. Appendix 3: Study Phases

11.3.1. Study Phases

Assessments and events will be classified according to the time of occurrence relative to dosing.

Study Phase	Definition
Pre-Treatment	Date < Date of First Dose
During Dosing	Date of First Dose <= Date <= Date of Final Dose + 1.
Post-dose to Week 6	Date of Final Dose + 1 < Date <= Date of Week 6 Visit ^[1] or Day 42 whichever is greater
Week 6 to Month 24	Date of Week 6 Visit ^[1] or Day 42 whichever is greater < Date <= Month 24 visit.
Safety Follow-up	Date > Month 24
[1] For participants who were consented Prior to Protocol Amendment 4, Day 42 will be used, as they will not have a Week 6 visit.	

Note: for any rule that is relative to dose, the term date also includes time, if recorded. The end date for a visit as recorded in the SV domain will be used for the determining study phase.

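### Table 3.15's time-normalised hypo- and hyperglycaemia rates keep, in each period, only subjects with both bounding visits, so partial follow-up is discarded and the treatment of patients without a Week 6 visit is unclear

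*SAP*

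**What the plan says.** Hypo- and hyperglycaemic events over Months 1-24 are a secondary efficacy endpoint (Protocol section 2; SAP 2.2 and 9.1.1). They are tabulated in Table 3.15 with shell EFF_T3 (SAP Appendix 11).

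- **Counts.** Footnote 1 defines the crude column: "Number of Events = the total number of events at each level of summarization". It states no visit condition, and none is stated for n (%).
- **Rates.** Footnote 2 divides each subject's events by the length of the period in 30-day months and restricts who counts: "Subjects are only included if they had both visits" bounding the period. The summary is an unweighted mean over subjects: "Mean = the average event rate reported by subject".
- **Periods.** After the any-time and dosing rows, the programming note says "Continue with Post-dose up to Week 6 Visit, Post Week 6 Visit to Month 3 Visit", then Months 3-6, 6-9, 9-12, 12-18 and 18-24. That makes nine rows.
- **Companion listing.** OTHER_L5 (Listing 44) has a different condition: "Duration of period and event rate will only be calculated if the visit at the end of the reporting period took place". It labels the overall period as running to the 24-month visit.
- **Week 6.** SAP 11.3.1, on study phases, says: "For participants who were consented Prior to Protocol Amendment 4, Day 42 will be used, as they will not have a Week 6 visit". EFF_T3 does not refer to this. The pooling rule in SAP 5.1 reads "For vital signs, haematology, clinical chemistry, biomarkers and Epstein-Barr virus serology, the time points Month 1 and Week 6 shall be combined"; glycaemic events are not in that list.

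**The concern.** These events are not visit measurements. Under the Time and Events Table (Protocol 6.2.2), patients enter them in a diary as they occur, with start and stop dates. Events and time at risk are therefore available up to last contact, and a rate does not need the closing visit. SAP 11.6.1 by default keeps all available planned data from withdrawn participants; footnote 2 overrides that for the rates and gives no reason.

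If subjects who leave or miss visits have a different event rate from those who attend, the rate column misdescribes the arm. Each exclusion removes one of 8 active subjects in a cohort. The count and rate columns of a row can also describe different subjects, and the shell has no separate n for the rate. Because table and listing use different conditions, the table cannot always be rebuilt from the listing.

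**Working it through.** The plan gives no figure for this table, so there is none to reproduce. The check takes the rule row by row and then sizes it.

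**Rows kept, out of nine (any time post-dose taken to end at Month 24)**

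| Attendance | Rows lost | Rows kept |
|---|---|---|
| Last visit Day 6 | 8 | 1 |
| Last visit Month 3 | 6 | 3 |
| Last visit Month 9 | 4 | 5 |
| Last visit Month 12 | 3 | 6 |
| Last visit Month 18 | 2 | 7 |
| Misses only Month 9, then returns | 6-9 and 9-12 | 7 |
| No Week 6 visit, literal reading | post-dose to Week 6, Week 6 to Month 3 | 7 |
| No Week 6 visit, Day 42 substituted | none | 9 |

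Missing only Month 9 costs the rates for Months 6 to 12, which is 6 of 24 months, despite continued follow-up. With no Week 6 visit, the literal loss runs from Day 6 to Day 90: 84 of 719 days (Day 1 to Day 720, 30-day months), or 12%.

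**Who lacks a Week 6 visit.** The number is not stated. Amendment 2 (2 April 2014) already describes a first infusion, about ten months before Amendment 4 (11 February 2015). Cohorts were dosed in sequence. A literal loss would therefore fall mainly on the earliest cohort or cohorts and their placebo patients. Of the 8 subjects on 9 mg, anywhere from 8 down to 0 could remain in the two Week 6 rows.

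**Size in the overall row.** All inputs except the arm size of 8 are assumptions: *k* leavers at Month 10, and completers at 2 events per month followed for 24 months. The completer-only mean is 2.0 whatever the leavers' rate *r*. The comparator is events per person-time:

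rate = [(8 − k) × 2 × 24 + k × r × 10] / [(8 − k) × 24 + k × 10]

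With leavers at twice the rate (*r* = 4):

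- k = 1: (336 + 40)/178 = 2.11; shortfall 1 − 2/2.11 = 5%
- k = 2: (288 + 80)/164 = 2.24; shortfall 11%
- k = 3: (240 + 120)/150 = 2.40; shortfall 17%

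With equal rates (*r* = 2) the comparator is 2.0 and there is no bias. With leavers at half the rate (*r* = 1) the direction reverses:

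- k = 1: (336 + 10)/178 = 1.94; completer-only mean 3% too high
- k = 3: (240 + 30)/150 = 1.80; completer-only mean 11% too high

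The follow-up discarded is 10 of 178, 20 of 164 and 30 of 150 person-months for k = 1, 2 and 3.

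**The case against.** The strongest reply is that little is lost and that the closing visit serves a purpose. Counts and n (%) still include these subjects, Listing 44 still prints their event numbers, and Figure 3.05 states no visit condition. From Month 3 on, the scheduled visits are the period boundaries, so a leaver's last contact is often the opening visit and adds almost no person-time to the next row. Requiring the closing visit also avoids treating unobserved time as event-free. Patients who stop treatment may keep the visit schedule (Protocol 4.5), so stopping need not mean a missed visit. The endpoint carries no formal hypothesis and is outside the MMRM.

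Most of this stands, and it limits the point. The gain lies mainly in the overall row, in the two early periods with contacts between their boundaries, and for subjects who miss a visit and return. Ending time at risk at last contact deals with unobserved time after a subject leaves.

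Three stronger readings are tempting, and the documents do not support them.

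- *The rule removes these patients from the analysis.* It acts per period and only on the rate.
- *Every patient consented before Amendment 4 is certainly excluded from the Week 6 rows.* SAP 11.3.1 classifies events as well as assessments and supplies Day 42, and OTHER_L5 labels its periods by weeks. Day 42 may well be intended; the shell does not say so.
- *The bias is 6% to 27%.* That follows from 1/((1 − p) + pk) − 1, where p is the share leaving and k is here their rate ratio: −5.9% at p = 0.125, k = 1.5, and −27.3% at p = 0.375, k = 2. The formula gives leavers the weight of a full period, which a person-time rate would not, and it shows one direction only.

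**Conclusion.** The point holds in limited form. As written, the rate column covers only subjects with both visits in each period. It drops early leavers from the overall rate and drops anyone who misses an intermediate visit from the two adjacent periods, although dated events are collected between visits. The overall-row statement assumes that the row ends at Month 24, which OTHER_L5 says and EFF_T3 does not.

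The illustrated size, 5% to 17% too low, rests on assumed leaver numbers, timing and a doubled event rate; the documents give none of these, and the sign depends on the last. The Week 6 matter is an ambiguity to close. The differing conditions in table and listing are a plain inconsistency. As the endpoint is descriptive, the impact is modest, but the correction is specific and needs no new data.

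**What to change.** 1. In EFF_T3 footnote 2, define the rate as events divided by observed time from the start of the period to the earlier of its end and last contact, including every subject who entered the period.
2. State that the Day 42 boundary of SAP 11.3.1 applies to EFF_T3 and OTHER_L5 where there was no Week 6 visit.
3. Use this one rule in both the table and the listing, and state in EFF_T3 where the overall period ends.
4. Show n and person-months beside each rate, and total events over total person-time by arm.

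The cost is revised shell wording and a small programming change. Individual rates become less stable when follow-up in a period is very short; the arm totals in item 4 address that.
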